Assessment of VSD closure will be conducted post device deployment during the procedure, at the post procedure follow-up visit, at the 30-day follow-up visit, at the six month follow-up visit, at the one year follow-up visit and at annual visits until the five year visit is complete. Investigators are required to record echocardiographic data to document closure status and submit the data to the sponsor on case report forms in the remote data entry system. An independent Echocardiography Board or Core Laboratory will review the one-year echocardiograms to verify closure status.

3. Follow-up Compliance Measures

Abbott (ABT) will have a dedicated staff to train and manage sites on the importance of protocol compliance, assist sites with reminders, and compensate sites to help ensure adequate subject follow-up. ABT will send reminders to each site regarding upcoming visits. Each enrolled subject will receive a visit notification card. Whenever possible, the site should schedule the next subject follow-up visit at the time of the current visit. Sites will be compensated for the time it takes for the investigator to complete the case report forms. As part of CRF completion reimbursement, sites will be compensated for time spent notifying and reminding subjects of upcoming follow-up visits. If a site becomes non-compliant, enrollment may be halted until the site initiates the appropriate steps to correct compliance.

Clinical Investigational Plan**4. Device Explant**

If a subject has a device explanted during the study, the timing of the explant determines whether the subject is followed further or discontinued from the study. If the device explant occurs before the 12-month visit and a Serious Adverse Event (SAE) is associated with the device explant, the subject will be discontinued on the date the device is explanted. (In this case, the subject is considered a failure for all endpoints except Technical Success.) If a device explant is not associated with a SAE, the subject will continue to be followed through the 12-month visit. The subject will then be discontinued at the 12-month visit.

If a subject has a device explanted after the 12-month visit, the subject will be discontinued on the date of the explant procedure.

J. Adverse Event Reporting

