Similarly, the three effectiveness objectives are the proportion of subjects who experience technical success, acute procedure success, and shunt closure success. In

[REDACTED]

Note: technical success analysis will include only prospectively enrolled subjects.

[REDACTED]

[REDACTED]

Clinical Investigational Plan

[REDACTED]

[REDACTED]

[REDACTED]

[REDACTED]

[REDACTED]

[REDACTED]

The analysis of technical success and acute procedure success will be conducted on all subjects who have an attempted device placement (defined as the delivery system enters the subject's body in an attempt to place a device). The analysis of shunt closure success will be conducted on the study population who has a 12-month follow-up visit. The serious adverse event endpoint will be evaluated on all subjects who have a 12-month follow-up visit or who had a serious adverse event prior to the 12-month visit. For all analyses, a secondary analysis will be conducted on the entire study population, including subjects that are classified as lost to follow-up. In the situation classified as lost to follow-up, subject's last known (reported) status will be used in the calculations.

[REDACTED]

[REDACTED]

Clinical Investigational Plan**III. Study Management****A. Investigators and Sites**

A list of institutions and investigators will be completed and sent to the FDA or other regulatory authorities upon request and as required by applicable regulations.

B. Monitoring Procedures

Monitoring will be conducted according to the ABT Clinical Monitoring standard operating procedure.

Prior to beginning the study, ABT will contact the investigator or designee to discuss the study and data requirements. An ABT monitor will periodically review the subject records and associated source documents.

The investigator shall make subject and study records available to the clinical monitor for monitoring.

C. Data**1. Source Data and Documentation**

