5.2 Descriptive Endpoints

The following descriptive safety endpoints will be summarized using descriptive statistics:

• All unadjudicated events

Statistical Analysis Plan

- All adjudicated events
- Serious (Major) adverse events
- Device related events
- Procedure related events
- Events unrelated to the device or the procedure
- Deaths

All variables will be summarized by frequency and percentage. This analysis will include all enrolled subjects.

The following descriptive non-safety endpoints will be summarized using descriptive statistics:

- Procedure duration
- Fluoroscopy duration
- Size of defect
- Access site
- Medication taken at the time of procedure
- Anesthesia type
- Number of VSDs
- VSD location

Continuous variables will be summarized by mean, standard deviation, minimum, and maximum. Categorical variables will be summarized by frequency and percentage. Missing data will be omitted.

5.3 **Overall Sample Size**

The total sample size required for evaluation of the primary safety endpoint and primary effectiveness endpoints is 80 subjects. In order to ensure 80 subjects to have either an endpoint or 12-month follow-up, 100 subjects will be enrolled. Additional subjects will be enrolled as necessary to attain 80 subjects for the primary safety endpoint analysis.

5.4 **Timing of Analysis**

The analyses for the final report will be conducted on a dataset locked after all enrolled subject have had the 60-month follow-up visit (excepting deaths, withdrawals and loss-to-follow-up before 60 months) or crossed the 60-moth visit window without a visit (missed visit).

6.0 **ADDITIONAL DATA**

6.1 **Demographic and Baseline Characteristics**

The demographic baseline variables to be summarized include, but are not limited to:

- Age
- Gender

Study Name: VPA, Version Date: 12Oct2016

Statistical Analysis Plan

- Medical history
 - Recurrent respiratory infections
 - o Contraindication to aspirin
 - Contraindication to anti-platelets
 - o Previous thromboembolic stroke
 - o Failure to thrive
 - o Cyanosis
 - Pulmonary hypertension
 - Irreversible pulmonary vascular disease
 - Previous cardiac surgery
- Active bacterial infection
- Clinical symptoms of congestive heart failure
- Sepsis

Age will be summarized by mean, standard deviation, minimum, and maximum. Other variables will be summarized by frequency and percentage. Missing data will be omitted.

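### Read literally, the visible primary shunt closure analysis leaves out SAE-associated explants that the protocol itself declares closure failures

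*Protocol*

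**What the plan says.** Three visible rules meet here.

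- **Closure population.** Protocol Section II (Statistical Analysis): "The analysis of shunt closure success will be conducted on the study population who has a 12-month follow-up visit". Section I.F and SAP 4.2.3 also tie the endpoint to the one-year visit. SAP 5.1.2.3 tests the rate against 58.7%.
- **Explants.** Protocol Section I.I.4 (Device Explant), on an explant before the 12-month visit that is associated with an SAE: "the subject will be discontinued on the date the device is explanted", and "the subject is considered a failure for all endpoints except Technical Success". Other explants before that visit are treated differently: "If a device explant is not associated with a SAE, the subject will continue to be followed through the 12-month visit".
- **Safety population.** The sentence in Section II that follows the closure rule takes subjects "who have a 12-month follow-up visit or who had a serious adverse event prior to the 12-month visit".

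Section II then adds: "For all analyses, a secondary analysis will be conducted on the entire study population, including subjects that are classified as lost to follow-up". On numbers, SAP 5.3 says "In order to ensure 80 subjects to have either an endpoint or 12-month follow-up, 100 subjects will be enrolled", and "Additional subjects will be enrolled as necessary to attain 80 subjects for the primary safety endpoint analysis".

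The closure population and closure sensitivity sentences in SAP 5.1.2.3 are cut off. Section II has redacted blocks both before and after the paragraph on analysis populations.

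**The concern.** I.I.4 sets a score for SAE-associated explants, and Section II sets the denominator in which closure scores are counted. Neither refers to the other in the visible text. A subject withdrawn at explant before 12 months has a closure score (failure) but no 12-month visit, and so has no place in the closure denominator as written. The safety set avoids this problem through its clause for earlier events; the closure set has no such clause.

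The direction of the effect is fixed. Every subject lost this way is a failure, so the observed closure rate can only rise, in the device's favour, in the analysis that decides the test against 58.7%.

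**Working it through.** **1. The plan's own figure.** SAP 5.3 enrols 100 to obtain 80. With the 80% follow-up level in SAP 3.0, 80 / (1 − 0.20) = 100, which reproduces. The 80 itself cannot be checked for closure, because alpha, power and the assumed rate are not visible.

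**2. Where each kind of subject falls, reading the visible text literally.**

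| Subject | Has a 12-month visit? | Safety set | Primary closure set | Closure score |
|---|---|---|---|---|
| Device in place, attends | yes | in | in | by residual shunt |
| Explant without SAE before 12 months | yes, followed to it | in | in | by residual shunt |
| Explant with SAE before 12 months | no, withdrawn at explant | in, through the SAE clause | **out** | **failure (I.I.4)** |

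Only the last row is inconsistent.

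**3. Size, as illustration only.** Inputs: limit p0 = 0.587 (SAP 5.1.2.3) and 80 subjects (SAP 5.3). Assumptions: an exact one-sided binomial test; alpha of 5% and 2.5%, since the level is redacted; and a range of explant counts e, since the documents give none. With k closures among n subjects, p(k, n) = P(Bin(n, 0.587) ≥ k).

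*Case A: explants are among the 80.* SAP 5.3 fills the 80 for the safety analysis, where these subjects count. Keeping them gives n = 80; dropping them gives n = 80 − e.

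| n | 80 | 79 | 78 | 77 | 76 |
|---|---|---|---|---|---|
| Explants dropped (e) | 0 | 1 | 2 | 3 | 4 |
| Closures needed, 5% | 55 | 55 | 54 | 53 | 53 |
| Closures needed, 2.5% | 56 | 56 | 55 | 55 | 54 |

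A decision changes only when the closure count lies from the number needed at 80 − e up to one below the number needed at 80.

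- e = 1: no count does so, at either alpha.
- e = 2: 54 at 5%; 55 at 2.5%.
- e = 3: 53 or 54 at 5%; 55 at 2.5%.
- e = 4: 53 or 54 at 5%; 54 or 55 at 2.5%.

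Examples with e = 4:

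- 53/80 = 66.3%, p = 0.103 kept; 53/76 = 69.7%, p = 0.032 dropped.
- 54/80 = 67.5%, p = 0.067 kept; 54/76 = 71.1%, p = 0.018 dropped.

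*Case B: 80 subjects have the visit and explants are additional.* Dropping them gives n = 80; keeping them gives n = 80 + e.

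- 5%, e = 1: 55/80 = 68.8%, p = 0.042 dropped; 55/81 = 67.9%, p = 0.057 kept.
- 2.5%, e = 1: 56/80 = 70.0%, p = 0.025 (0.0247) dropped; 56/81 = 69.1%, p = 0.035 kept.
- Away from the limit: 60/80 = 75.0%, p = 0.0017. At 5% it survives eight added failures (60/88, p = 0.043) and is lost only with nine (60/89, p = 0.058).

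**The case against.** The strongest reply is that the documents already say how these subjects are scored. I.I.4 is a specific rule. For safety it adds little, because an SAE-associated explant before 12 months is ordinarily a safety event anyway. Its real work is on acute procedure success and shunt closure. Dropping the subjects would cancel the rule for closure, so the natural reading is a general population sentence with a specific exception. The wording in SAP 5.3 about having an endpoint or 12-month follow-up leans the same way. This is a good argument about intent, and it may well be right. It does not change the denominator sentence, which carries no exception although the safety sentence next to it does.

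The second reply is redaction. The reconciling clause could be in a hidden block of Section II or in the cut-off text of SAP 5.1.2.3. That stands in full. A reader might infer that the SAP omits these subjects; the documents do not support that, because its population text cannot be seen. Any amendment must be conditional.

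Third, the secondary analysis covers everyone, so a gap between the two results should show. That is true and useful, but the analysis is labelled secondary and does not alter the primary test.

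Fourth, the effect is small. That also stands: in case A, which follows from SAP 5.3, a single explant changes nothing. Only case B makes one explant decisive.

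A reader might also infer that explants without an SAE are mishandled. No contradiction is shown there. They are followed to the 12-month visit, the residual-shunt criterion applies, and I.I.4 limits automatic failure to the SAE-associated group.

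**Conclusion.** The point holds as a conflict within the visible protocol text. Section I.I.4 declares SAE-associated explants before 12 months to be closure failures, and the Section II population sentence, read literally, removes them from the primary closure analysis. The bias has one direction and favours the device. It is worth fixing because the repair is a single clause that restores the sponsor's own rule.

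Its size is unknown, because no explant count is given. Under the assumed exact one-sided test at 5% or 2.5%, it matters only for results close to the limit: no decision changes with one explant inside the 80, one or two closure counts are affected with two to four, and a single explant can decide the result only if explants are additional to 80 visits.

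It may be tempting to state an inflated type I error. The documents do not support a figure: the closure denominator of the High Risk Cohort behind 58.7% is not visible, so the error rate under either definition cannot be established. Confidence is medium, since the hidden text may already settle the matter.

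**What to change.** Unless the unredacted text already does this, define the primary closure set in Protocol Section II as subjects with a 12-month follow-up visit or with an SAE-associated device explant before it, and count those explants as closure failures, as I.I.4 already states. Make the same change in SAP 5.1.2.3 if its wording differs. If the hidden text already includes these subjects, a cross-reference between Section II and I.I.4 is enough.

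No new data are needed. There are two costs. The closure rate will be slightly less favourable if any such explants occur. The sponsor must also check how the High Risk Cohort closure rate behind 58.7% handled them: if that rate used only subjects with a 12-month visit, the two denominators would no longer match, and the difference would have to be stated or the limit re-derived on the same basis.

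No change is proposed for explants without an SAE or for acute procedure success.

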2.0 TRIAL OBJECTIVES

The primary safety objective is to evaluate the proportion of subjects experiencing a serious adverse event within 12 months of the procedure.

The effectiveness objective is to evaluate the proportion of subjects who experience technical success, acute procedure success, and shunt closure success.

3.0 TRIAL DESIGN

This is a prospective, non-randomized, multi-site clinical trial designed to evaluate the safety and effectiveness of the AMPLATZER Muscular VSD Occluder. The primary safety and effectiveness endpoints of this trial are intended to be evaluated against the corresponding endpoints of the High Risk Cohort of the Muscular VSD trial.

This study will enroll a maximum of 100 subjects at a maximum of 50 sites in the United States and additional sites in Europe and Canada. Each study subject receiving a device will be followed for 60 months post-procedure, unless the device is explanted. If subject follow-up drops below 80%, additional subjects will be enrolled to ensure a final population of 80 subjects either meet a defined endpoint or will be followed for five years.

A subject is considered enrolled in the trial after he/she has provided informed consent, meets all inclusion criteria, meets no exclusion criteria, and the delivery system enters the subject's body in an attempt to implant the AMPLATZER Muscular VSD Occluder (Implant Attempt). A subject could be enrolled in the trial prospectively or retrospectively (refer to CIP Section I.H).

4.0 TRIAL ENDPOINTS

4.1 **Primary Safety Endpoint**

The primary safety endpoint is the proportion of subjects experiencing a serious adverse event (SAE) within 12 months of the procedure.

Page **4** of **12**

ST. JUDE MEDICAL

Statistical Analysis Plan

4.2 **Primary Effectiveness Endpoints**

There are three primary effectiveness endpoints including technical success, acute procedure success, and shunt closure success.

4.2.1 Primary Effectiveness Endpoint 1: Technical Success

Primary effectiveness endpoint 1 is the proportion of subjects who have technical success. Technical success is defined as a device is successfully deployed in the ventricular septal defect.

4.2.2 Primary Effectiveness Endpoint 2: Acute Procedure Success

Primary effectiveness endpoint 2 is the proportion of subjects who have acute procedure success. Acute procedure success is defined as a defect with \leq two millimeters residual shunt at the time of the post procedure evaluation.

4.2.3 Primary Effectiveness Endpoint 3: Shunt Closure Success

Primary effectiveness endpoint 3 is the proportion of subjects who have shunt closure success. Shunt closure success is defined as a defect with \leq two millimeters residual shunt at the one-year follow-up visit.

4.3 **Descriptive Endpoints**

The trial has a number of descriptive endpoints. See Sections 5.2 for a full listing.

5.0 **STATISTICAL METHODS**

5.1 **Primary Endpoints**

This trial has one primary safety endpoint and three primary effectiveness endpoints.

5.1.1 Primary Safety Endpoint

The primary safety endpoint is the proportion of subjects experiencing a serious adverse event (SAE) within 12 months of the procedure.

5.1.1.1 Hypothesis

Let π_{SAE} be the probability of subjects experiencing a serious adverse event within 12 months of the procedure. In the high risk cohort of the muscular VSD trial, **serious adverse** event in the intent-to-treat population experienced a serious adverse event. Since the subject selection criteria will be similar to that used in the High Risk Cohort of the Muscular VSD Occluder trial, π_{SAE} will be compared against the observed major adverse event rate from the High Risk Cohort with a margin of **serious**.

Statistical Analysis Plan

The following hypothesis will be tested:

 $H_0: \pi_{SAE} \ge 63.2\%$ $H_a: \pi_{SAE} < 63.2\%$

5.1.1.2 Analysis Method

The probability of π_{SAE} will be estimated as a	. The hypothesis will be tested at the
significance level.	

5.1.1.3 Sample Size

The primary safety endpoint event rate within 12 months of	

5.1.1.4 Analysis Population

The analysis of the primary safety endpoint will

5.1.1.5 Sensitivity Analysis

Statistical Analysis Plan

5.1.2 Primary Effectiveness Endpoints

5.1.2.1 Primary Effectiveness Endpoint 1: Technical Success

Primary effectiveness endpoint 1 is the proportion of subjects who have technical success. Technical success is defined as a device is successfully deployed in the ventricular septal defect.

Hypothesis

The probability of π_{Tech} will be estimated . The hypothesis will be tested at the significance level. The null hypothesis will be rejected

Sample Size

Analysis Population

The analysis of the technical success effectiveness endpoint will include all prospectively enrolled subjects who have an attempted device placement (defined as the delivery system enters the subject's body in an attempt to place a device).

ST. JUDE MEDICAL

Statistical Analysis Plan

5.1.2.2 Primary Effectiveness Endpoint 2: Acute Procedure Success

Primary effectiveness endpoint 2 is the proportion of subjects who have acute procedure success. Acute procedure success is defined as a defect with \leq two millimeters residual shunt at the time of the post procedure evaluation.

Hypothesis

Let π_{Acute} be the probability of subjects who have acute procedure success.

the acute procedure success rate π_{Acute} will be compared against

The following hypothesis will be tested:

 $H_0: \pi_{Acute} \leq 61.3\%$

 $H_a: \pi_{Acute} > 61.3\%$

Analysis Method

The probability of π_{Acute} will be estimated

Sample Size

The acute procedure success rate is assumed to be

Analysis Population

The analysis of the acute procedure success effectiveness endpoint will

5.1.2.3 Primary Effectiveness Endpoint 3: Shunt Closure Success

Primary effectiveness endpoint 3 is the proportion of subjects who have shunt closure success. Shunt closure success is defined as a defect with \leq two millimeters residual shunt at the one-year follow-up visit.

Statistical Analysis Plan

Hypothesis

Let π_{Close} be the probability of subjects who have shunt closure success.

	the shunt closure success rate π_{Close} will be compared against the shunt
closure success rate	
The following hypothesis will be	tested:

 H_0 : $π_{Close}$ ≤ 58.7%

H_a: π_{Close} > 58.7%

Analysis Method

The probability of π_{Close} will be estimated

Sample Size

Analysis Population

The analysis of the shunt closure success effectiveness endpoint will include

Sensitivity Analysis

A sensitivity analysis will be carried out to include

5.2 Descriptive Endpoints

The following descriptive safety endpoints will be summarized using descriptive statistics:

• All unadjudicated events

Statistical Analysis Plan

- All adjudicated events
- Serious (Major) adverse events
- Device related events
- Procedure related events
- Events unrelated to the device or the procedure
- Deaths

All variables will be summarized by frequency and percentage. This analysis will include all enrolled subjects.

The following descriptive non-safety endpoints will be summarized using descriptive statistics:

- Procedure duration
- Fluoroscopy duration
- Size of defect
- Access site
- Medication taken at the time of procedure
- Anesthesia type
- Number of VSDs
- VSD location

Continuous variables will be summarized by mean, standard deviation, minimum, and maximum. Categorical variables will be summarized by frequency and percentage. Missing data will be omitted.

5.3 **Overall Sample Size**

The total sample size required for evaluation of the primary safety endpoint and primary effectiveness endpoints is 80 subjects. In order to ensure 80 subjects to have either an endpoint or 12-month follow-up, 100 subjects will be enrolled. Additional subjects will be enrolled as necessary to attain 80 subjects for the primary safety endpoint analysis.

5.4 **Timing of Analysis**

The analyses for the final report will be conducted on a dataset locked after all enrolled subject have had the 60-month follow-up visit (excepting deaths, withdrawals and loss-to-follow-up before 60 months) or crossed the 60-moth visit window without a visit (missed visit).

6.0 **ADDITIONAL DATA**

6.1 **Demographic and Baseline Characteristics**

The demographic baseline variables to be summarized include, but are not limited to:

- Age
- Gender

Study Name: VPA, Version Date: 12Oct2016

Statistical Analysis Plan

- Medical history
 - Recurrent respiratory infections
 - o Contraindication to aspirin
 - Contraindication to anti-platelets
 - o Previous thromboembolic stroke
 - o Failure to thrive
 - o Cyanosis
 - Pulmonary hypertension
 - Irreversible pulmonary vascular disease
 - Previous cardiac surgery
- Active bacterial infection
- Clinical symptoms of congestive heart failure
- Sepsis

Age will be summarized by mean, standard deviation, minimum, and maximum. Other variables will be summarized by frequency and percentage. Missing data will be omitted.

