If the delivery system enters the subject's body in an attempt to place a device but no device is implanted during the initial procedure, the subject will be discontinued from the study after a 30-day adverse event collection period. This subject will be discontinued from the study even if Re-intervention occurs within the 30-day period.

If the subject signs a consent form, but the delivery system does not enter the subject, the subject will be considered a consented screen failure, for which a discontinuation form must be completed.

If a subsequent catheterization procedure is performed to attempt to close a residual shunt or new muscular VSD with an Amplatzer Muscular VSD Occluder, this will be classified as a Re-intervention. Data regarding Re-intervention(s) will be captured on new Baseline/Procedure forms for all subjects who meet Technical Success at the initial implant procedure. All follow-up visits will be calculated based on the initial procedure date.

Clinical Investigational Plan

Table 1: Main Data Requirements

	Pre-Procedure	Procedure	Post procedure (+ one day)	30 days (+/- 7 days)	6 Months (+/- 30 days)	One Year (+ 60 days)	Two Year (+/- 180 days)	Three Year (+/- 180 days)	Four Year (+/- 180 days)	Five Year (+/- 180 days)
Physical Exam	✓		✓	✓	✓	✓	✓	✓	✓	✓
ECG	✓		✓	✓	✓	✓	✓	✓	✓	✓
Echo ¹	✓		✓	✓	✓	✓	✓	✓	✓	✓
Cardiac catheterization		✓								
TEE or ICE		✓								
AE Assessment		✓	✓	✓	✓	✓	✓	✓	✓	✓
Chest X-ray AP and lateral	✓		✓			✓	✓	✓	✓	✓
Fluoroscopy ²						✓	✓	✓	✓	✓

¹ Echocardiographic data at Baseline/Procedure can include TTE, TEE and/or ICE.

Echocardiographic image data must be submitted to the sponsor for one year visits.

² Fluoroscopy required if chest x-rays are read as “uncertain” with regard to wire fracture.

1. Implant Procedure

Reference the Amplatzer Muscular VSD Occluder and Delivery System Instructions for Use (IFU) for implant procedure techniques. The Amplatzer Muscular VSD Occluder is to be implanted percutaneously by catheter technique.

2. Closure Assessment

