6.3 Mortality

The number of deaths will be summarized.

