6.4 Adverse Events

Adverse events, serious adverse events and unanticipated adverse device effects (UADE) will be summarized in terms of number of events, the percentage of subjects with events.

ST. JUDE MEDICAL

Statistical Analysis Plan

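### Late safety events are reported as crude percentages of all enrolled subjects although some leave follow-up early, so late-event risk is biased downward

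*SAP*

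**What the plan says.** SAP 5.2 lists descriptive safety endpoints that include serious events, device-related events, procedure-related events and deaths, and then states: "All variables will be summarized by frequency and percentage. This analysis will include all enrolled subjects". SAP 6.4 says that adverse events "will be summarized in terms of number of events, the percentage of subjects with events". SAP 6.3 gives deaths as a count only: "The number of deaths will be summarized". On timing, SAP 5.4 says: "The analyses for the final report will be conducted on a dataset locked after all enrolled subject have had the 60-month follow-up visit".

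Follow-up is not the same for everyone in that denominator:

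- Enrolment (Protocol I.H, SAP 3.0) occurs when the delivery system enters the body, so failed implants count as enrolled.
- SAP 3.0: "Each study subject receiving a device will be followed for 60 months post-procedure, unless the device is explanted".
- If no device is implanted at the initial procedure (Protocol, Study Procedure and Assessments): "the subject will be discontinued from the study after a 30-day adverse event collection period".
- Device explant (Protocol, Device Explant). Before 12 months and associated with an SAE, follow-up ends at explant. Before 12 months without an SAE, it ends at the 12-month visit. After 12 months: "the subject will be discontinued on the date of the explant procedure".
- SAP 3.0 adds subjects only if follow-up falls below 80%, and SAP 5.3 enrols 100 to obtain 80 with an endpoint or 12-month follow-up.

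SAP 5.2, 5.4, 6.3 and 6.4 show no visible redaction. None of them names a time-to-event method, a person-time rate, a visit-specific denominator or a confidence interval.

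**The concern.** A percentage over all enrolled subjects estimates cumulative risk only if everyone is observed to the same horizon. Here a subject who leaves at 30 days or 12 months stays in the denominator and cannot add to the numerator afterwards. Compared with complete follow-up, the percentage can only be lower. That direction needs no assumption about why subjects leave.

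The bias matters most for late events, which are what years two to five of follow-up add. The study's stated purpose is to further evaluate safety and effectiveness, and a reader of the final report will probably take percentages from a 60-month lock as five-year risks. There is a precision problem as well. With about 100 subjects, a bare percentage hides wide uncertainty, and these sections plan no interval.

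**Working it through.** **The plan's own figure.** SAP 5.3 enrols 100 to obtain 80. This matches a 20% shortfall: 80 / (1 − 0.20) = 100. It is the only stated figure that bears on attrition, and it is not in dispute.

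**Inputs that are assumptions.** The documents give no five-year event rates, no expected share of failed implants or explants, and no timing of loss. I take:

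- a true five-year risk of 10%, with 5% as a check;
- a share *n* whose follow-up ends at 30 days;
- a share *l* lost uniformly between months 1 and 60;
- loss unrelated to risk;
- a share *e* of the five-year risk falling at the procedure, the rest following a constant hazard.

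**Formula.** With F(t) the true cumulative risk at month t, the expected crude percentage is

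crude = n·F(1) + l·mean[F(t), t = 1 to 60] + (1 − n − l)·F(60).

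**Worked case (true risk 10%, e = 0, n = 10%, l = 10%, so total exits equal the tolerated 20%).**

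- Monthly hazard = −ln(0.90)/60 = 0.001756.
- F(1) = 1 − exp(−0.001756) = 0.00175.
- Mean F over months 1 to 60 = 1 − (0.99825 − 0.90)/(59 × 0.001756) = 0.0517.
- crude = 0.10 × 0.00175 + 0.10 × 0.0517 + 0.80 × 0.10 = 0.0002 + 0.0052 + 0.0800 = 0.0853, or 8.5%.

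**Range for a true 10%.**

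| Ended at 30 days | Lost over months 1–60 | Constant hazard | Half of risk at procedure | 80% of risk at procedure |
|---|---|---|---|---|
| 5% | 0 | 9.5% | 9.8% | 9.9% |
| 10% | 0 | 9.0% | 9.5% | 9.8% |
| 0 | 20% | 9.0% | 9.5% | 9.8% |
| 10% | 10% | 8.5% | 9.3% | 9.7% |
| 20% | 0 | 8.0% | 9.0% | 9.6% |
| 10% | 20% | 8.1% | 9.0% | 9.6% |

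The shortfall is 0.1 to 2.0 percentage points, or about 1% to 20% in relative terms. The last row has 30% total exits, which is more than the tolerated 20%. The 8.0% does not depend on it, but needs all of the 20% to leave at 30 days. For a true 5%, the last row gives 4.0% (constant hazard) to 4.8% (80% at procedure).

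**Precision.** If 8 of 100 subjects have an event, the exact 95% interval is about 3.5% to 15.2%.

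**The case against.** Several points on the other side stand:

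- **How many leave by rule.** A reader might infer that follow-up ends early by rule for many subjects. The documents do not support that. The rules cover failed implants and explants only, and no expected number is given for either. Retrospective subjects were already implanted, so failed implants should come essentially from the prospective part. Ordinary loss may contribute as much or more.
- **How large the loss is.** A reader might posit heavy loss such as 40%. Nothing in the plan points to that, and SAP 3.0 adds subjects when follow-up falls below 80%. SAP 5.3 ties its 80 to 12 months, so larger five-year loss is not strictly excluded, but it would be the reader's own assumption.
- **Constant hazard is near the worst case.** Procedure-related events cluster early. With 80% of risk at the procedure, a true 10% is understated by only 0.1 to 0.4 points.
- **Endpoints differ.** A subject discontinued at an SAE-associated explant is already counted for any SAE; only later events or death are missed. A subject without a device has little or no continuing exposure to device-related events, so counting that subject as event-free is then largely right. Simple Kaplan-Meier censoring would give that subject the risk of those who still carry a device. Explant is also plausibly informative.
- **Status of the endpoints.** They are descriptive. SAP 5.2 names no five-year estimand; the horizon comes from the lock in SAP 5.4. SAP 6.3 plans a count of deaths, so the percentage of deaths arises only from SAP 5.2.
- **Redaction.** Much of Protocol Section II is blacked out, so a long-term method there cannot be ruled out.

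These points limit the size and shape the remedy. They do not make an all-enrolled denominator suitable for late events. Nor does the Protocol's secondary analysis using last known status: it again counts subjects who were event-free at last contact as event-free.

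**Conclusion.** The concern holds in limited form. Crude percentages of all enrolled subjects, from data locked at 60 months with unequal follow-up, understate late-event risk. The direction is certain wherever an enrolled subject leaves early while still at risk. The size is not known from the documents. With non-informative loss and the same risk for all subjects, a true 10% would be reported as about 8.0% to 9.9%. The effect is small for periprocedural events and largest for late deaths and late SAEs. For device-related events, the model overstates the part due to subjects without a device.

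A reader might infer that the trial's main safety conclusion is compromised. It is not. The primary safety endpoint is at 12 months and has its own population in Protocol Section II (a 12-month visit, or an SAE before it), which this wording does not touch. The change is still worth making, because it gives a better estimate than the stated method at little cost.

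**What to change.** In SAP 5.2, 6.3 and 6.4, keep the planned counts and add:

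1. Kaplan-Meier estimates for death.
2. Cumulative incidence, with death as a competing event, for SAE and device-related SAE.
3. 95% confidence intervals and numbers at risk at 12 and 60 months for each of these.
4. Device-related estimates based on implanted subjects, with explant handled as a competing event or reported separately.
5. Delayed entry at consent, or separate reporting, for retrospectively enrolled subjects. Protocol I.H requires their consent and the potential for one-year and five-year data, so patients who died early tend to be left out. Kaplan-Meier from the procedure date would not correct that.
6. A table of the number and timing of rule-based discontinuations (no device implanted, explant) and of other losses.

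The cost is SAP wording and a few extra tables from event and exit dates that the study should already hold. No visit, follow-up rule or primary test changes. The downside is that the reported percentages become slightly less favourable. The new estimates still assume that ordinary loss is unrelated to risk, and the SAP should say so.
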